## Protocol for non-interventional studies based on existing data

Document Number:	c31688667-01
BI Study Number:	0135-0343
BI Investigational Product(s):	Actilyse
Title:	Temporal trends of thrombolysis treatment in Chinese acute ischemic stroke (AIS) patients from 2007-2017: analysis of China National Stroke Registry (CNSR) I, II, and III
Protocol version identifier:	1.1
Date of last version of protocol:	12 Mar 2020
PASS:	No
EU PAS register number:	EUPAS33970
Active substance:	Alteplase
Medicinal product:	Actilyse
Product reference:	Not applicable
Procedure number:	Not applicable
Joint PASS:	No
Research question and objectives:	
Primary objectives:
 
 
• To investigate the temporal changes in the proportion of intravenous recombinant plasminogen activator (IV-rtPA) treatment from 2007 to 2017 among intravenous thrombolytics (IVT)-eligible patients and overall AIS patients in China;
 
• To investigate the temporal changes in IV-rtPA treatment time intervals from 2007 to 2017 among IV-rtPA-treated patients in China.
 
 
Secondary objectives:
 
 
• To describe the demographic and clinical characteristics of the IV-rtPA-treated patients, IVT-eligible patients and the overall AIS patients from the CNSR I to III.
 

Proprietary confidential information © 2020 Boehringer Ingelheim International GmbH or one or more of its affiliated companies

Country(-ies) of study:	China
Author:	[REDACTED]
Marketing authorisation holder(s):	[REDACTED]
MAH contact person:	Not applicable
In case of PASS, add: <EU-QPPV:>	Not applicable
In case of PASS, add: <Signature of EU-QPPV:>	Not applicable
Date:	17 Apr 2020
Page 1 of 39	
Proprietary confidential information © 2020 Boehringer Ingelheim International GmbH or one or more of its affiliated companies. All rights reserved. This document may not - in full or in part - be passed on, reproduced, published or otherwise used without prior written permission	

## 2. LIST OF ABBREVIATIONS

ADRs	Adverse Drug Reactions
AEs	Adverse Events
AIS	Acute Ischemic Stroke
BI	Boehringer Ingelheim
CI	Confidence Interval
CRC	Clinical Research Coordinators
CRF	Case Report Form
CROs	Contract Research Organizations
CNSR	China National Stroke Registry
CT	Computed Tomography
DSMB	Data Safety and Management Board
DTN	Door to Needle
ECASS	European Cooperative Acute Stroke Study
EDC	Electronic Data Capture
██████████	██████████
ESOC	European Stroke Organization Conference
GPP	Good Pharmacoepidemiology Practices
H	Hours
ICFs	Informed Consent Forms
ICH	Intracranial Hemorrhage
IEC	Independent Ethics Committee
IRB	Institutional Review Board
IS	Ischemic Stroke
IV-rtPA	Intravenous Recombinant Plasminogen Activator
IVT	Intravenous Thrombolytics
Min	Minutes
MOH	Ministry of Health
MRA	Magnetic Resonance Angiography
MRI	Magnetic Resonance Imaging
NCRC-ND	National Clinical Research Center for Neurological Diseases
NIHSS	National Institutes of Health Stroke Scale
PRF	Paper-based Registry Forms

SAH	SubArachnoid Hemorrhage
SAP	Statistical Analysis Plan
SD	Standard Deviation
SOPs	Standard Operation Procedures
TIA	Transient Ischemic Attack

## 4. ABSTRACT

Name of company: Boehringer Ingelheim			
Name of finished medicinal product: Actilyse			
Name of active ingredient: Alteplase			
Protocol date: 17 Apr 2020	Study number: 0135-0343	Version/Revision: 1.1	Version/Revision date: 12 Mar 2020
Title of study:	Temporal trends of thrombolysis treatment in Chinese acute ischemic stroke patients (AIS) from 2007-2017: analysis of China National Stroke Registry (CNSR) I, II, and III		
Rationale and background:	Based on the conclusion from the European Cooperative Acute Stroke Study (ECASS) III study, the Chinese treatment guideline for AIS was updated in 2010, with intravenous recombinant plasminogen activator (IV-rtPA) treatment recommendation time window extended from within 3h of symptom onset to 4.5h. In addition, efforts have been taken by the government and academic societies to develop stroke centers and stroke care quality control networks. In order to understand the impact of these efforts on the clinical practices for AIS treatment in China, we plan to evaluate the 10-year temporal changes from 2007-2017, in the IV-rtPA treatment proportion and treatment time intervals of AIS patients by using the CNSR I, II, and III. In addition, the demographic and clinical characteristics of the AIS patients will be described.		
Research question and objectives:	
Primary objectives:
 
 
• To investigate the temporal changes in the proportion of intravenous recombinant plasminogen activator (IV-rtPA) treatment from 2007 to 2017 among intravenous thrombolytics (IVT)-eligible patients and overall AIS patients in China;
 
• To investigate the temporal changes in IV-rtPA treatment time intervals from 2007 to 2017 among IV-rtPA-treated patients in China.
 
 
Secondary objectives:
 
 
• To describe the demographic and clinical characteristics of the IV-rtPA-treated patients, IVT-eligible patients and the overall AIS patients from the CNSR I to III.
 
		
Study design:	This is a non-interventional study based on existing data from the CNSR.		

Name of company: Boehringer Ingelheim			
Name of finished medicinal product: Actilyse			
Name of active ingredient: Alteplase			
Protocol date: 17 Apr 2020	Study number: 0135-0343	Version/Revision: 1.1	Version/Revision date: 12 Mar 2020
Population:	
All eligible patients from the CNSR I to III will be included. Patient groups include the overall AIS patients (patient group A), IVT-eligible patients (patient groups B and B'), and IV-rtPA-treated patients (patient groups C and C').
 
The in- and exclusion criteria for the reporting groups are listed below:
 
1) All AIS patients (patient group A)
 
1. Inclusion criteria:
 
 
(1) Aged 18-80 years
 
(2) Diagnosed with AIS on admission
 
 
2. Exclusion criteria:
 
 
(1) Missing baseline data including age and gender
 
(2) Diagnosed with intracranial intracranial hemorrhage (ICH), Transient Ischemic Attack (TIA), subarachnoid hemorrhage (SAH), or unspecific stroke
 
(3) Arrived at hospital after 7 days of symptom onset
 
 
2) IVT-eligible patients (patient groups B and B')
 
1. Inclusion criteria:
 
 
(1) Met the in- and exclusion criteria of "all AIS patients"
 
(2) Arrived at hospital within 2h (patient group B) or 3.5h (patient group B') of symptom onset
 
 
2. Exclusion criteria:
 
 
(1) Missing key data including 
 
i. symptom onset time (or last known well time);
 
ii. hospital arrival time;
 
iii. whether received IVT treatment or not;
 
iv. the time of IVT treatment.
 
 
 
(2) Documented IVT absolute contraindications, according to the case report form (CRF) for each wave of CNSR (please refer to ANNEX 3 for details)
 
 
3) IV-rtPA-treated patients (patient groups C and C')
		

Name of company: Boehringer Ingelheim			
Name of finished medicinal product: Actilyse			
Name of active ingredient: Alteplase			
Protocol date: 17 Apr 2020	Study number: 0135-0343	Version/Revision: 1.1	Version/Revision date: 12 Mar 2020

1. Inclusion criteria:
 
 
(1) Met the in- and exclusion criteria of “IVT-eligible patients”
 
(2) Treated with IV-rtPA within 3h (patient group C) or 4.5h (patient group C') of symptom onset
 
 
2. Exclusion criteria:
 
 
(1) Not received IVT
 
(2) Received IVT other than rtPA
 
(3) Treated with IV-rtPA after 3h (patient group C) or 4.5h (patient group C') of symptom onset
 
(4) Received additional treatments with intra-arterial reperfusion or experimental therapies
 
			
Variables and co-variables:	
Primary outcomes: For all the three waves of CNSR, the following primary outcomes will be assessed:
 
 
● Proportion of patients who received IV-rtPA treatment within 3h of symptom onset (patient group C) among 2hr IVT-eligible patients (patient group B);
 
● Proportion of patients who received IV-rtPA treatment within 4.5h of symptom onset (patient group C') among 3.5h IVT-eligible patients (patient group B').
 
 
Secondary outcomes: the analysis will be performed for each wave of CNSR
 
Among all AIS patients (patient group A), the following secondary outcomes will be assessed:
 
 
● Proportion of patients who arrived at hospital within 2h of symptom onset and who received IV-rtPA treatment within 3h of symptom onset (patient group C);
 
● Proportion of patients who arrived at hospital within 3.5h of symptom onset and who received IV-rtPA treatment within 4.5h of symptom onset (patient group C');
 
 
Among 3h IV-rtPA-treated patients (patient group C), the following secondary outcomes will be assessed:
 
 
● The door-to-needle (DTN) time (time between arrival at hospital and the administration of IV-rtPA treatment);
 
		

Name of company: Boehringer Ingelheim		
Name of finished medicinal product: Actilyse		
Name of active ingredient: Alteplase		
Protocol date: 17 Apr 2020	Study number: 0135-0343	Version/Revision: 1.1
Version/Revision date: 12 Mar 2020		


● Proportion of patients DTN time <math>\leq</math> 60 minutes (min);

● Time between symptom onset and arrival at hospital;

● Time between symptom onset and the administration of IV-rtPA treatment.

 
Among 4.5h IV-rtPA-treated patients (patient group C'), the following secondary outcomes will be assessed:
 

● The DTN time;

● Proportion of patients DTN time <math>\leq</math> 60 min;

● Time between symptom onset and arrival at hospital;

● Time between symptom onset and the administration of IV-rtPA treatment.

		
    		

Name of company: Boehringer Ingelheim			
Name of finished medicinal product: Actilyse			
Name of active ingredient: Alteplase			
Protocol date: 17 Apr 2020	Study number: 0135-0343	Version/Revision: 1.1	Version/Revision date: 12 Mar 2020
[REDACTED]			

Name of company: Boehringer Ingelheim										
Name of finished medicinal product: Actilyse										
Name of active ingredient: Alteplase										
Protocol date: 17 Apr 2020	Study number: 0135-0343	Version/Revision: 1.1								
Data sources:	CNSR I, II, and III									
Study size:	
It was estimated that in CNSR I, II, and III, the number of total AIS patients is 14704, 19604, and 15204, respectively.
 
Assuming the IV-rtPA-treated among IVT-eligible patients in CNSR I, II, and III are 4%, 5%, and 28% with the 95% confidence interval (CI) for each wave as below, then which can be distinguished with current study size.
 
  
 CNSR	Wave I	Wave II	Wave III	
   
 Assumed IV-rtPA proportion among eligible patients % (95% CI)	4% (3.7-4.3%)	5% (4.7-5.3%)	28% (27.3-28.7%)	
  
		CNSR	Wave I	Wave II	Wave III	Assumed IV-rtPA proportion among eligible patients % (95% CI)	4% (3.7-4.3%)	5% (4.7-5.3%)	28% (27.3-28.7%)
CNSR	Wave I	Wave II	Wave III							
Assumed IV-rtPA proportion among eligible patients % (95% CI)	4% (3.7-4.3%)	5% (4.7-5.3%)	28% (27.3-28.7%)							
Data analysis:	
The study is descriptive in nature. For continuous data, descriptive statistics (number of patients, mean, standard deviation [SD], minimum, median, interquartile range, and maximum) will be presented. Categorical data will be presented as frequency and proportion with 95% CI as appropriate.
 
[REDACTED]
									
Milestones:	
Feasibility assessment: Jun 2019
 
Protocol finalization: Dec 2019
 
Statistical and epidemiological analysis plan: Mar 2020
 
Start of data collection: NA
 
End of data collection: NA
 
Statistical and epidemiological analysis report finalization: Mar 2020
 
Final results: Apr 2020
 
Clinical study report finalization: Apr 2020
 
Final report of the study result: Apr 2020
									

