**2) IVT-eligible patients (patient groups B and B')**

1. Inclusion criteria:

- (1) Met the in- and exclusion criteria of "all AIS patients"
- (2) Arrived at hospital within 2h (patient group B) or 3.5h (patient group B') of symptom onset

2. Exclusion criteria:

- (1) Missing key data including
  - i. symptom onset time (or last known well time);
  - ii. hospital arrival time;
  - iii. whether received IVT treatment or not;
  - iv. the time of IVT treatment
- (2) Documented IVT absolute contraindications, according to the case report form (CRF) for each wave of CNSR (please refer to [ANNEX 3](#) for details)

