**3) IV-rtPA-treated patients (patient groups C and C')**

1. Inclusion criteria:

- (1) Met the in- and exclusion criteria of "IVT-eligible patients"
- (2) Treated with IV-rtPA within 3h (patient group C) or 4.5h (patient group C') of symptom onset

2. Exclusion criteria:

- (1) Not received IVT
- (2) Received IVT other than rtPA
- (3) Treated with IV-rtPA after 3h (patient group C) or 4.5h (patient group C') of symptom onset
- (4) Received additional treatments with intra-arterial reperfusion or experimental therapies

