## **9.7 DATA ANALYSIS**

### **9.7.1 Main analysis**

[figure not shown]
For continuous data, descriptive statistics (number of patients, mean, standard deviation (SD), minimum, median, interquartile range, and maximum) will be presented. Categorical data will be presented as frequency and proportion with 95% CI. Unless otherwise stated, the calculation will be based on the available data. No data imputation will be performed for the missing data. Details for all analyses will be provided in the statistical analysis plan (SAP).

[REDACTED]

[REDACTED]

[REDACTED]

[REDACTED]

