## **9.9 LIMITATIONS OF THE RESEARCH METHODS**

The quality of a study based on existing data relies on accuracy of recorded data. Important data may not be available. The hospitals participating in the CNSR, although spread throughout China and covered all geographic areas, were mainly selected by convenience in nature. These hospitals possess more resources and expertise in ischemic stroke when compared to other hospitals in China, especially those at a country-level or lower ranks. Therefore, results from the current study will have to be interpreted with caution as it is not known what proportion of stroke patients in China have access to hospital cares at a level similar to those participated in the CNSR. Due to the nature of explore existing data, the interpretation is based on non-missing data.

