10.2 HANDLING OF MISSING VALUES

Every reasonable attempt have been undertaken to ensure completeness of data collection. In general, missing data will be treated as missing. No data imputation will be performed for the missing data. The amount of missing data will be reported and its effect on potentially bias conclusions will be assessed. Due to the nature of existing data, the interpretation is based on non-missing data.

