11.1 MAIN ANALYSIS

Patient group A includes patients aged 18-80 years and diagnosed with AIS on admission. Patients with missing baseline data including age and gender and diagnosed with intracranial hemorrhage (ICH), Transient Ischemic Attack (TIA), subarachnoid hemorrhage (SAH), or unspecific stroke and arrived at hospital after 7 days of symptom onset will be excluded.

Patient group B and patient group B' are both based on patient group A. And patients with missing key data will be excluded from patient group B and patient group B', including symptom onset time or last known well time, hospital arrival time, whether received IVT treatment or not and the time of IVT treatment.

Patients documented with IVT absolute contraindications, according to the case report form (CRF) for each of CNSR will be also excluded from patient group B and patient group B'.

Patients group B included patients who arrived at hospital within 2h of symptom onset.

[figure not shown]
Patients group B' included patients who arrived at hospital within 3.5h of symptom onset.

Patient group C is based on patients group B and patient group C' is based patient group B'. And both patient group C and patients group C' are to meet the inclusion criteria of "IVT-eligible patients". Patients not received IVT or received IVT other than rtPA or received additional treatments with intra-arterial reperfusion or experimental therapies will be excluded. Patients group C included patients who were treated with IV-rtPA within 3h. Patients group C' included patients who were treated with IV-rtPA within 4.5h.

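### In the all-AIS proportions C/A and C'/A, a treated patient with a missing key item counts as not treated, and the SAP conflicts on whether such patients stay in group A

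*Protocol*

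**What the plan says.** **Outcome.** Among all AIS patients (group A), the plan reports per wave the "Proportion of patients who arrived at hospital within 2h of symptom onset and who received IV-rtPA treatment within 3h of symptom onset" and the 3.5h/4.5h equivalent (Protocol Abstract and 9.3.2.2; SAP 8.2.2 and 11.1.2). These are listed as secondary outcomes, although primary objective 1 names the overall AIS population.

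**Denominator.** Group A's missing-data exclusion reads "Missing baseline data including age and gender". Treatment status and times are not named.

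**Numerator.** Groups B and B' exclude patients missing onset time, arrival time, "whether received IVT treatment or not", or the time of IVT (Protocol 9.2). SAP 11.1 ties this to B and B' alone: "patients with missing key data will be excluded from patient group B and patient group B" (the second group named is B'). The first criterion for C and C' begins "Met the in- and exclusion criteria of" and points to the IVT-eligible group, so C and C' inherit the exclusion.

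**Conflicting text.** SAP 10.3 lists the same four items in one exclusion list with age and gender, non-qualifying diagnoses and arrival after 7 days. It names no patient group.

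**General rules.** Protocol 9.7.1: "No data imputation will be performed for the missing data". SAP 10.2: "In general, missing data will be treated as missing". Protocol 9.9: "the interpretation is based on non-missing data". SAP 10.2 also undertakes to report how much is missing and to assess its effect, without giving a method. SAP Table 3.1 shows n/N, % and 95% CI per wave, with no line for unknown status.

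**The concern.** The numerator of C/A needs four data items that the denominator does not. A patient who was given IV-rtPA in time, but whose form lacks one of them, is therefore counted with the untreated. C/B and C'/B' drop the same patient altogether, so the two halves of primary objective 1 handle one record in opposite ways.

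A constant loss would lower every wave by the same factor and leave relative trends intact. A loss that changes between waves produces an apparent trend with no change in care. Such a difference is possible: data capture went from paper forms (CNSR I) to a web CRF (II) to an EDC system (III). Because SAP 10.3 points to another denominator, two analysts could also print different versions of Table 3.1 from the same data.

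**Working it through.** **1. The plan's own figures.** None is given for C/A. The only computed figures are the 95% CIs in Protocol 9.5. With p ± 1.96·√(p(1−p)/N) and N the total AIS count:
- 4%, N = 14704: 3.68–4.32%
- 5%, N = 19604: 4.69–5.31%
- 28%, N = 15204: 27.29–28.71%

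These match after rounding. They are labelled as proportions of eligible patients and make no allowance for missing data, so they serve below for scale only.

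**2. Where each kind of record goes.**

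| Record, otherwise meeting group A | C/B, C'/B' | C/A, C'/A under Protocol 9.2 and SAP 11.1 | C/A, C'/A if SAP 10.3 applies to A |
|---|---|---|---|
| Treated in window, eligible, a key item missing | Dropped | Denominator only: wrongly untreated | Dropped |
| Known untreated, onset or arrival time missing | Dropped | Denominator only: correct | Dropped |
| IVT status unknown, recorded late arrival or contraindication | Not in B or B' | Denominator only: correct, cannot be in C or C' | Dropped |
| IVT status unknown, could otherwise qualify | Dropped | Denominator only: wrong if in fact treated in window | Dropped |

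The error comes from row 1 and from the truly treated part of row 4.

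**3. Size with all of A in the denominator.** Let t be the true proportion and m the share of truly treated, qualifying patients with a missing item. Observed C/A = t(1−m). If t does not change, the apparent CNSR III/I ratio is (1−m₃)/(1−m₁). Every m is an assumption.

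| m₁ | m₃ | Ratio |
|---|---|---|
| 5% | 5% | 0.95/0.95 = 1.00 |
| 5% | 1% | 0.99/0.95 = 1.04 |
| 10% | 2% | 0.98/0.90 = 1.09 |
| 15% | 2% | 0.98/0.85 = 1.15 |
| 20% | 5% | 0.95/0.80 = 1.19 |
| 2% | 10% | 0.90/0.98 = 0.92 |
| 5% | 20% | 0.80/0.95 = 0.84 |

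**4. Size if SAP 10.3 removes the patients from A.** With m_T and m_U the missing shares among treated and other patients, observed = t(1−m_T) / [t(1−m_T) + (1−t)(1−m_U)]. Take t = 2% (assumed).
- Missingness unrelated to treatment, 20% in CNSR I and 5% in III: 2.00% in both waves, ratio 1.00. With all of A kept: 1.60% to 1.90%, ratio 1.19.
- Only needle times missing, so m_U = 0, with m_T 10% and 2%: 0.018/0.998 = 1.804% and 0.0196/0.9996 = 1.961%, ratio 1.087. With all of A kept: 1.80% and 1.96%, ratio 1.089. Removal hardly helps, because a needle time can be missing only in someone who was treated.
- Missing only among the others, m_T = 0 and m_U = 20%: 0.02/0.804 = 2.49% against a true 2.00%. Keeping all of A gives exactly 2.00%.

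Neither rule is right under every pattern of missingness.

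**5. Scale.** Protocol 9.5 assumes 4%, 5% and 28%; these are C/B-type figures, borrowed only for comparison. CNSR I to II is a ratio of 5/4 = 1.25. An artefact of 1.089 to 1.188 between two waves would be 0.089/0.25 = 36% to 0.188/0.25 = 75% of that excess. CNSR I to III is 28/4 = 7; producing it from missing data alone, with none missing in CNSR III, needs m₁ = 1 − 1/7 = 86%. At t = 2% with 14704 and 15204 patients, a two-sided 5% comparison of CNSR I with III would flag the 10%/2% and 20%/5% artefacts with probability 17% and 51%. The visible plan contains no such test; this only shows how the artefact compares with sampling error.

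**The case against.** The strongest reply is that the denominator is not settled. SAP 10.3 reads as study-wide. Group A's wording is open-ended about baseline data. Arrival within 7 days cannot be confirmed without onset and arrival dates. Calculations are said to use available data. All of this stands, and it is why the point includes a conflict to be resolved. It does not remove the problem: step 4 shows that losing treated patients without a needle time survives the SAP 10.3 reading.

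Several stronger readings are tempting, and the documents do not support them:
- That every patient with a gap is misclassified. A known-untreated patient lacking a time is rightly counted as untreated.
- That moving to EDC raised the proportions. The documents show a change of tool, not of completeness. They describe coordinators, monitoring and completeness checks for all three forms of capture (Protocol 9.6, SAP 12). The direction is unknown.
- That the plan breaks its no-imputation rule. No imputation step is planned. The effect follows from nested groups, though it sits badly with treating missing data as missing.
- That the plan has no safeguard. SAP 10.2 promises an assessment, Protocol 9.9 states the limitation, and parts of the analysis text and mock tables are redacted. One can say only that the visible text gives no method, no split by wave and no bounds.

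**Conclusion.** The point holds for C/A and C'/A. Under Protocol 9.2 and SAP 11.1, truly treated, in-window, eligible patients with a missing key item are scored as not treated, and SAP 10.3 contradicts the denominator that those sections imply. If that loss differs between waves, the all-AIS trend is biased, upward or downward. Under the assumed shares the spurious CNSR III/I ratio runs from 0.84 to 1.19, with 1.00 when losses are equal; the true shares are not in the documents. A reader might infer that a several-fold rise could be an artefact of data capture. It could not, short of losing about 86% of treated patients in CNSR I. A change of the order assumed between CNSR I and II could be materially distorted. The correction is worth making because it is cheap and primary objective 1 depends on these figures.

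**What to change.** 1. Reconcile SAP 10.3 with SAP 7.2 and 11.1, and state one rule for whether patients with missing key data remain in group A.
2. In Table 3.1, report per wave the number in A with each key item missing, split by recorded IV-rtPA, no IVT and unknown status.
3. Print C/A and C'/A in three versions:
   - all of A in the denominator, as the lower bound;
   - patients of unknown IVT status removed from the denominator;
   - an upper bound that counts as treated in window both the recorded IV-rtPA patients lacking a time and the unknown-status patients, except those whose recorded data rule them out of C or C' (late arrival, late treatment, contraindication). Counting only the recorded IV-rtPA patients would not be an upper bound, since unknown-status patients would still count as untreated.
4. Describe a wave-to-wave change in the all-AIS proportion as robust to missing data only if its direction holds across these versions. This is a rule for wording, not a test, and fits a descriptive study.

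The cost is some SAP text and a few table rows from data items the registries already collected. The downside is that a secondary result appears as a range. If a redacted section already contains such an analysis, only item 1 and a cross-reference are needed.
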